⁸ Urine pregnancy testing will be carried out at all visits, excluding the option 3 & option 4 screening visit which will be a serum pregnancy test. Women aged ≥45 years will receive a urine pregnancy test at the STRIDE Week 24 visit in lieu of an FSH test which will be conducted at Month 1, if required.

⁹ Subject will be excluded at the Investigator's discretion for alcohol/drug dependency. Use for medical reason is acceptable with prescription evidence.

¹⁰ FSH for females aged ≥45 years not confirmed as post-menopausal in the STRIDE study (FSH not conducted at STRIDE Week 24 visit, see footnote 5).

¹¹ There must be a minimum of 4 weeks between the screening and baseline 12MWT.

	STRIDE Week 24	STRIDE Week 24	STRIDE Week 24	X ¹	X ¹
Eye examination					X ¹
Wrist radiograph ²					X
DXA Scan ³	STRIDE Week 24	STRIDE Week 24	STRIDE Week 24	STRIDE Week 24	X
Concomitant Medication review	STRIDE Week 24	STRIDE FU	STRIDE FU	X	X
AE Review ⁴	STRIDE Week 24	STRIDE FU	STRIDE FU	X	X
Dispense Study Drug	X	X	X	X	X
First dose of study drug ⁵	X	X	X	X	X

¹ Eye examination can be done at any time between the screening and baseline visit for scheduling reasons.

² Subjects <25 years old.

³ Optional. Only conducted at sites which participated in the DXA sub-study. If a DXA scan was performed at STRIDE Week 24 it will be regarded as the baseline. Sites with approvals in place should review all subjects against the additional protocol criteria (Section 4.3) and perform DXA if subject eligible and not performed in STRIDE.

⁴ Review of pre-treatment events for subjects enrolling at option 3 and option 4: after exiting STRIDE or REN001-101, and nDNA-PMM subjects.

⁵ Subject enrolling at STRIDE Week 24 should take the first dose the day after the Baseline visit, this will be confirmed with a telephone call from site the next day. Subject enrolling at STRIDE FU or after exiting STRIDE or Study REN001-101, and nDNA-PMM subjects should take the first dose at the study centre baseline visit.

Table 3: Schedule of Activities

Assessments/Time*	Screening / Baseline Visits ¹	Month 1 (Day 28)	Month 3 (Day 84)	Month 6 (Day 168)	Month 9 (Day 252) Germany only	Month 12 (Day 336)	Month 15 (Day 420) Germany only	Month 18 (Day 504)	Month 24 (Day 672) or pre M24 Early Withdrawal ²	Month 30 (Day 840), M36 (Day 1008), M42 (Day 1176)	Month 48 (Day 1344) or post M24 Early Withdrawal ²
Window for visit		±3 days	±7 days	±7 days	±21 days	±21 days	±21 days	±21 days	±21 days	±21 days	±21 days

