8.4. VISIT WINDOWS

Data will be assigned to ‘analysis’ visits using windowing (see table below). If more than one assessment (including the early termination or unscheduled assessments) falls within the same defined window, the on-treatment assessment closest to the target day with non-missing data will be used for analysis. If the scheduled visit assessment is on-treatment and within the analysis window, then this will be used irrespective of other unscheduled assessments within the analysis window. If two assessment dates are at the same distance from the target day, the latest on-treatment assessment with non-missing data will be used for analysis. Off-treatment assessments will only be assigned to a visit window in the absence of an on-treatment assessment within the analysis window.

This is the same approach as used in the REN001-201 SAP and therefore the REN001-201 data will have the same analysis visit windowing assigned as per the REN001-201 CSR.

To assess whether a REN001-202 visit is within the analysis window the day relative to the start of REN001-202 will be used. This will mean that for subjects who enrol at REN001-201 FU the interruption in study drug during the REN001-201 FU period will be ignored.

Study	Original Visit	Visit Name for Combined Study Summaries	Target Day ¹	Protocol Visit Window	Analysis Window ¹	Analysis Interval
REN001-201	Baseline	Baseline	1	NA	≤1*	NA
	Week 2	Month 0.5	14	±3	8 – 20	13 (±6)
	Week 4	Month 1	28	±3	21 – 35	15 (±7)
	Week 12	Month 3	84	±7	63 – 105	43 (±21)
	Week 18	Month 4.5	126	±7	106 – 146	41 (±20)
	Week 24	Month 6	168	±7	147 – 189	43 (±21)
REN001-202	Baseline	Month 6	1	NA	≤1*	NA
	Month 1	Month 7	28	±3	21 – 35	15 (±7)
	Month 3	Month 9	84	±7	63 – 105	43 (±21)
	Month 6	Month 12	168	±7	147 – 189	43 (±21)
	Month 9 [^]	Month 15 [^]	252	±21	211 – 293	83 (±41)
	Month 12	Month 18	336	±21	294 – 378	85 (±42)
	Month 15 [^]	Month 21 [^]	420	±21	379 – 461	83 (±41)
	Month 18	Month 24	504	±21	462 – 546	85 (±42)
	Month 24	Month 30	672	±21	630 – 714	85 (±42)
	Month 30	Month 36	840	±21	798 – 882	85 (±42)
	Month 36	Month 42	1008	±21	966 – 1050	85 (±42)
	Month 42	Month 48	1176	±21	1134 – 1218	85 (±42)
	Month 48	Month 54	1344	±21	1302 – 1386	85 (±42)

NA=not applicable.

¹ Target day and analysis windows are relative to start of each study.

* Baseline values must be prior to dosing if time of assessment is recorded.

[^] Month 9 and Month 15 (original) visits are only applicable for German sites.

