If a subject does not have a record for a visit and did not withdraw from the study, then the record will be counted as due to missing. For subjects who withdraw from the study then the date of study withdrawal will be used to assess whether the subject missed the visit. Any missing records prior to this date will be classed as missing and any missing records after this date will be classed as a withdrawal.

For interim reporting some subjects will still be ongoing in REN001-202 at the time of the data cut, so in addition to the above categories the number of subjects with the potential to reach a REN001-202 visit will be included; and therefore, the number who attended, missed or were withdrawn prior to visit will be based on those with the potential to reach the REN001-202 visit. Subjects will be assessed as to whether they have the potential to reach a REN001-202 visit using the duration from the first dose in REN001-202 to the date of the data cut. If the duration is greater than the target visit day, then the subject will be deemed to have the potential to reach the REN001-202 visit. If the subject attends a visit they will automatically be categorized as having the potential to reach the visit.

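### At interim cuts, SAP 9.1 counts a visit as missed when the subject has not yet been seen but the protocol visit window is still open

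*SAP*

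**What the plan says.** SAP 9.1 provides a by-visit table of subjects who attended, missed, or withdrew before each visit. For interim cuts it adds the number with the potential to reach each REN001-202 visit, assessed "using the duration from the first dose in REN001-202 to the date of the data cut". The test is: "If the duration is greater than the target visit day, then the subject will be deemed to have the potential to reach" that visit. There is one addition: "If the subject attends a visit they will automatically be categorized as having the potential to reach the visit". The counts then rest on this group: "the number who attended, missed or were withdrawn prior to visit will be based on those with the potential to reach the REN001-202 visit".

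The rule for a missed visit is: "If a subject does not have a record for a visit and did not withdraw from the study, then the record will be counted as" missing. Nothing in the section sets aside a subject whose visit is still allowed to happen.

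Protocol Table 3, in the row "Window for visit", and SAP 8.4 both give ±3 days for Month 1, ±7 days for Months 3 and 6, and ±21 days from Month 9 onward (Months 9 and 15 in Germany only). The SAP 8.4 analysis windows extend further, to between 7 and 42 days after target. SAP 2 and SAP 13 set the interim cut at the last subject's last visit in REN001-201, when REN001-202 subjects will be at different points of follow-up.

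**The concern.** The purpose of a potential-to-reach count is to keep subjects out of the denominator until they could reasonably have been seen. A threshold at the target day does not do this, because a visit on any later day in the window is fully compliant. The rule is also lopsided. A subject who comes early enters as attended, while one booked late but in window enters as missed.

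The table goes into the interim synoptic CSR for the regulatory submission. SAP 2 names informative missing data as a key limit on interpreting long-term results, and the attendance table is one place where a reader would judge how much is missing. Misses created by the counting rule weaken that table.

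**Working it through.** The plan gives no figure to reproduce. The check sets the SAP 9.1 threshold against the windows, then illustrates the size.

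**Exposed days.** Take duration as cut date minus first-dose date plus 1, the convention SAP 9.5 uses for treatment duration; SAP 9.1 does not define it. A subject is then due from target + 1 and still in window to target + *w*.

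| Visit | Target day | *w* | Due but in window | Analysis window ends |
|---|---|---|---|---|
| Month 1 | 28 | 3 | 29–31 | 35 |
| Month 3 | 84 | 7 | 85–91 | 105 |
| Month 6 | 168 | 7 | 169–175 | 189 |
| Month 12 | 336 | 21 | 337–357 | 378 |
| Month 18 | 504 | 21 | 505–525 | 546 |
| Month 24 | 672 | 21 | 673–693 | 714 |

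Months 9, 15, 30, 36, 42 and 48 also have 21 such days. Without the +1, each span is one day shorter.

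**Expected counts.** The 150 mtDNA-PMM subjects come from SAP 3.5. Assumptions not in the documents: first doses spread evenly over *E* = 365 to 730 days, visit days spread evenly over target ± *w*, no withdrawals, no true misses, and enrolment reaching past the window. Up to 50 nDNA-PMM subjects are left out.

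- In the exposed span: 150 × *w*/*E*. For *w* = 21 this is 8.6 (*E* = 365) to 4.3 (*E* = 730); for *w* = 7, 2.9 to 1.4; for *w* = 3, 1.2 to 0.6.
- Not yet seen at the end of day target + *u*: probability (*w* − *u*)/(2*w* + 1). Summed over *u* = 1 to *w* this is *w*(*w* − 1)/[2(2*w* + 1)], which is 210/43 = 4.88, 21/15 = 1.40 and 3/7 = 0.43 for *w* = 21, 7 and 3.
- Wrongly counted as missed (multiply by 150/*E*): 2.0 to 1.0 for *w* = 21, 0.6 to 0.3 for *w* = 7, 0.2 to 0.1 for *w* = 3.

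**Percentages.** In continuous time the false misses for a ±21 visit are 21/4 = 5.25 days' worth of enrolment. Early attenders add another 5.25 to the denominator, so the share is 5.25/(*E* − target + 5.25).

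- Month 12, *E* = 730: 5.25/399.25 = 1.3%, about 1.1 of 82 subjects.
- Month 12, *E* = 540: 5.25/209.25 = 2.5%, about 1.5 of 58.
- Month 12, *E* = 365: 5.25/34.25 = 15.3%, about 2 of 14.
- Month 18, *E* = 540: 5.25/41.25 = 12.7%, about 1.5 of 11.

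**Comparing rules.** Now assume a true miss rate of 10%, at Month 12 with *E* = 365. Enrolment then covers 29 days past target (365 − 336), of which 8 lie past the closed window (365 − 357). Of the 21 open days after target, 21 − 5.25 = 15.75 would be attended if nobody missed.

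- Current rule: missed 29 − 0.9 × (8 + 15.75) = 7.625; denominator 29 + 0.9 × 5.25 = 33.725; 22.6%.
- Later threshold (target + 21) with attenders still added: missed 0.1 × 8 = 0.8; denominator 8 + 0.9 × 21 = 26.9; 3.0%.
- Closed windows only: 0.8/8 = 10%, the assumed truth.

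**The case against.** The best reply is that this is small and transient. Withdrawals with reasons, and subjects still ongoing, have their own rows in SAP 9.1, and a false miss changes neither. The problem cannot arise at the final CSR, which follows completion by all subjects, and no hypothesis test is planned. The number with potential to reach each visit is to be shown, so a small denominator would be visible. All of this stands.

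Even spread across the window is also probably pessimistic, since Protocol Section 6 asks for the target day where possible. If visit days were triangular around target, 5.25 becomes 21/6 = 3.5, a third lower. If they were normal with SD 7 days, it becomes 7/√(2π) = 2.79, about 47% lower. The 365-day case at Month 12 then falls from about 15% to about 11% or 9%. That reduces the size but leaves the mechanism.

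A reader might infer that the rule makes retention look worse the longer subjects are on drug. The documents do not support this. Retention is read from the withdrawal and ongoing rows. The expected number of false misses is the same at every ±21-day visit that enrolment has comfortably passed; only the percentage rises, as the denominator shrinks. A reader might also infer that every in-window subject is counted as missed, but those already seen are counted correctly as attended.

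**Conclusion.** The point holds as a defect in a stated counting rule. Within the window after the target day, a compliant subject not yet seen is put in the interim denominator and classed as missed. The likely size is about 0 to 2 subjects per visit, on the assumptions of 150 subjects, even enrolment over 365 to 730 days and even visit timing. The documents give no enrolment span. Shares of 12.7% to 15.3% arise only when the assumed span ends 29 to 36 days past the target day, so they should not be read as a forecast. The error inflates missed visits in interim attendance summaries and goes no further. It is worth correcting because the table supports a submission and the correction is cheap.

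**What to change.** In SAP 9.1, base the interim attended, missed and withdrawn percentages on subjects whose protocol window has closed by the cut: duration from first REN001-202 dose to the cut greater than target day plus 3, 7 or 21 days, as applies to the visit. Define duration with the +1 day convention. The thresholds become Day 31, 91, 175, 357, 525 and 693 for Months 1, 3, 6, 12, 18 and 24, and so on. Because the clock runs to the cut for everyone, withdrawn subjects stay in.

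Remove the automatic inclusion of attenders from this denominator. Moving the threshold while keeping that clause would admit open-window subjects only if they attended, and would understate misses (3.0% against a true 10% in the example above). Show subjects whose window is still open as two separate counts: already attended, and not yet seen.

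The cost is a short text edit, a small program change and a smaller denominator at the latest visit. At Month 12 with a 540-day span it falls from about 58 to about 51 of 150 (183 × 150/540). Where the latest visit has only just been reached the drop is larger, from about 14 to about 3 with a 365-day span (8 × 150/365), but the remaining subjects stay visible in the open-window counts. No new data are needed.

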9.2. DEMOGRAPHIC AND BASELINE CHARACTERISTICS

Demography (sex, race, ethnicity, age at consent [years], weight, height, body mass index (BMI) at screening and menopausal status) will be summarized. Age, weight, height and BMI will be summarized using summary statistics for continuous variables. Sex, categorical age (18 – 25 years, 26 – 45 years and 46 – 64 years and \geq 65 years), race, ethnicity, and menopausal status (men, pre-menopausal women and post-menopausal women) will be summarized as categorical variables.

The appropriate baseline will need to be used for the subject dependent on their starting position (REN001-201 or REN001-202). For example, the summary of age at consent from the start of REN001 treatment will take their REN001-201 age at consent for subjects who received mavodelpar in REN001-201 and their REN001-202 age at consent for all other subjects.

All subgroups defined in [Section 8.5](#) will be summarized as categorical variables. In addition, the following baseline endpoints will be summarized as continuous variables:

- 12MWD – baseline distance
- PROMIS T-score
- MFIS scale – physical, cognitive, psychosocial and total score
- PGI-S – muscle and fatigue (note, summarized as categorical variables only)

The duration of PMM symptoms (years) will be summarized using summary statistics for continuous variables.

Duration of PMM symptoms (years) = Age at consent – Age at onset of PMM symptoms

These data will be summarised for the safety and DXA scan sets. Menopausal status will only be summarized for the DXA scan set.

9.3. MEDICAL HISTORY AND CONCOMITANT DISEASES

Medical history for subjects who enrol at REN001-201 W24 or FU will come from REN001-201. The only changes to their medical history will be the updating of information (e.g., provision of an end date).

Medical history will be coded using Medical Dictionary for Regulatory Activities (MedDRA) version 23.1.

Medical history will be presented for each safety set by System Organ Class (SOC) and Preferred Term (PT) with counts and percentages. Each subject will be counted only once in each SOC or SOC/PT summary. In the summary tables, medical history will be presented by decreasing frequency of subjects overall within each SOC and then similarly by decreasing frequency of subjects overall within each PT. In cases of SOCs or PTs with equal frequencies, medical history will be sorted alphabetically.

The following PTs, which are associated with the disease under study, will be listed but excluded from the summaries:

- mitochondrial myopathy
- progressive external ophthalmoplegia
- MELAS syndrome

- myoclonic epilepsy and ragged-red fibres
- Kearns-Sayre syndrome
- gene mutation
- mitochondrial DNA deletion
- mitochondrial encephalomyopathy.

9.4. PRIOR AND CONCOMITANT MEDICATIONS

Prior and concomitant medications will be coded using World Health Organization (WHO) Drug Dictionary version WHODRUG GLOBAL B3 September 1, 2020.

Prior medications and concomitant medications are defined in the table below based on the summary being presented.

Presentation	Prior Medication ^a	Concomitant Medication ^a
from start of REN001-201	Medications started prior to the first administration of study drug in REN001-201	Medications taken following first administration of study drug in REN001-201. Medications will be attributed to a treatment period (REN001-201 or REN001-202) if they start or continue into the treatment period.
from start of REN001	Medications started prior to the first administration of mavodelpar ^b	Medications taken following first administration of mavodelpar.
From start of REN001-202	Medications started prior to first administration of study drug in REN001-202 ^b	Medications taken following first administration of study drug in REN001-202

^a Medications started before receiving the study dose but continuing after will be considered as both prior and concomitant medications.

^b For subjects who participated in REN001-201 only ongoing medications at the time of starting dosing in REN001-202 will be considered as prior medications. Note, from start of REN001 this is relevant only to REN001-201 placebo subjects.

Medication will be summarised for each safety set and the DXA scan set by anatomic therapeutic chemical (ATC) level 2 (therapeutic main group) and ATC level 5 (PT medication name) with counts and percentages. Prior and concomitant medications will be presented by descending frequency in ATC and PT within ATCs over all subjects. A

subject who takes more than one medication will be counted only once if these medications belong to the same extended ATC classification. These summaries will be repeated for medications that have an adverse impact or positive impact on the bones; a medical review of unique medications will be performed prior to database lock to identify these medications.

All data will be listed, and variables will be included to identify the phase of the study when the medication starts and ends (prior, REN001-201 or REN001-202).

If either the start or stop date of medication is missing, the most conservative case will be considered when assigning medications to categories. For a missing start date where stop date is after start date of dosing or missing, the date will be imputed as the dosing start date for the study that the medication was reported in. For a missing start date where stop date is on or before the start date of dosing, the date will be imputed as the day before the stop date and the event will be classified as a prior medication for the study it was reported in. For a missing stop date the date will be imputed as the last study date for REN001-202, except for medications recorded in REN001-201 where the subject enrolls after exiting REN001-201; in these cases the last study date in REN001-201 will be used. If a partial date is recorded, the following convention will be used to assign the medication based on the database that the medication was recorded in:

- If a partial date is missing a start day and the month/year is the same as the start date of dosing then use the dose start date if the stop date is after the dose start date or the stop date is missing, else '01' will be used for the day; if a start date is missing a month and the year is the same as the start date of dosing then use the dose start date if the stop date is after the dose start date or the stop date is missing, else January will be used for the start month.
- If a partial date is missing a stop day and month/year is same as last study date then use last study date, else last day of the given month will be used for the stop day; if a stop date is missing a month and the year is the same as last study date then use last study date, else December will be used for the stop month.

Concomitant non-drug therapies will also be listed and the associated phases (prior, REN001-201 or REN001-202) will be included.

9.5. TREATMENT EXPOSURE

Duration of mavodelpar treatment, days on mavodelpar treatment, number of mavodelpar capsules taken, and mavodelpar treatment compliance, will be summarized for each safety analysis set using descriptive statistics. Duration of treatment will also be summarized using 1 month categories up to 3 months and then 3 monthly (84 days) categories (e.g., ≤ 1 month, >1 to ≤ 2 months, >2 to ≤ 3 months, ≤ 3 month, >3 to ≤ 6 months, ..., >51 to ≤ 54

months, >54 months); and treatment compliance will also be summarized using the categories <80%, 80-120% and >120%.

- Duration of treatment in days is defined as (date of last mavodelpar dose minus date of first mavodelpar dose plus 1 day). Values will be presented to 1 decimal place
- Days on treatment is defined as the duration of treatment minus the number of days the subject is instructed to not take their mavodelpar medication (e.g., dose interruption due to AE); this will also include the gap in study medication for subjects enrolling at REN001-201 FU
- Number of capsules expected to be taken is defined as the days on mavodelpar treatment multiplied by the number of capsules to be taken each day (2 per day)
- Number of capsules taken is defined as number of capsules dispensed minus number of capsules returned for mavodelpar treatment period
- Treatment compliance (%) is defined as $100 * \text{number of mavodelpar capsules taken} / (\text{number of REN001 capsules expected to be taken})$. Values will be presented to 1 decimal place.

If study drug is not returned, the listing will present a compliance range; the lower limit will assume no study drug taken for the containers not returned and, the upper limit will assume all study drug taken for the containers not returned. The compliance listing will also include number of capsules dispensed and number of capsules returned for mavodelpar treatment period. If study drug is not returned the summary will consider number of capsules taken as missing, and so the subject will be excluded. However, for the treatment compliance categorical summary, the subject may be counted if their range falls entirely within one treatment compliance category (e.g., if the range is 40-60% they will be counted in the count for the <80% category).

As the study will be ongoing at the time of the interim synoptic CSR only duration of treatment and days on treatment will be presented. For ongoing subjects, the date of last dose will be assigned the date of last contact up to the date of the data cut.

Only mavodelpar dosing across the 2 studies will be listed.

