5 STUDY DRUG

5.1 Study Drug Identity

Study drug is presented as orange, hard gelatin capsules, manufactured by Xcelience LLC, a Lonza company. The dosage strength of REN001 capsules is 50mg. Capsules are packaged in 200mL high-density polyethylene (HDPE) bottles, with a heat induction seal and child-resistant lids, containing 100 capsules of 50mg REN001. Labels will contain batch number and expiration date.

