5.7 Compliance

At all study visits subject compliance with the study drug regimen will be monitored by capsule counts. If a subject consistently fails to take their study drug, the Investigator should alert the site monitor, Medical Monitor and Sponsor and a decision will be made as to whether the subject should be withdrawn for non-compliance.

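### Subjects with any unreturned study drug drop out of the mean and median of capsules taken and compliance, although the SAP already derives bounds that could keep them in

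*SAP*

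**What the plan says.** SAP 9.5 (Treatment Exposure) works with one total per subject: "Number of capsules taken is defined as number of capsules dispensed minus number of capsules returned for mavodelpar treatment period". Compliance is that total divided by the capsules expected, at two per day on treatment. Both are summarized with descriptive statistics for each safety analysis set, and compliance is also banded as below 80%, 80–120% and above 120%.

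Three rules cover unreturned drug:

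- **Listing:** "If study drug is not returned, the listing will present a compliance range". For this range "the lower limit will assume no study drug taken for the containers not returned", and the upper limit assumes everything in them was taken.
- **Continuous summary:** "If study drug is not returned the summary will consider number of capsules taken as missing, and so the subject will be excluded".
- **Banded table:** "for the treatment compliance categorical summary, the subject may be counted if their range falls entirely within one treatment compliance category".

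On the protocol side, bottles are described as "containing 100 capsules of 50mg REN001" (Protocol 5.1). Protocol 5.6 requires subjects to bring back all drug, empties included, at each visit. Protocol 5.7 adds: "At all study visits subject compliance with the study drug regimen will be monitored by capsule counts". Neither document gives an expected rate of non-return or an expected number of exclusions.

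**The concern.** The rule is all-or-nothing at subject level, while the counting is done bottle by bottle over four years. A subject with 31 bottles accounted for and one missing is treated like a subject with no counts at all. The chance of at least one gap rises with time in study, so the rule bears most on the longest-treated subjects, who matter most to a long-term safety study.

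If returning containers is related to taking the drug, the reported mean and median compliance describe a selected group. The final report is where this matters: SAP 9.5 omits compliance from the interim synoptic report, so the main compliance summary comes when gaps have had the longest time to accumulate.

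**Working it through.** The plan states no figure to reproduce, so the check rebuilds the bottle count and then shows how the rule behaves over a range of assumed loss rates.

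**Inputs.** 100 capsules per bottle (Protocol 5.1); 2 capsules per day (Protocol 5.3); enough bottles to cover each interval between visits (Protocol 5.2); Month 48 = Day 1344, with dispensing at baseline and Months 3, 6, 12, 18, 24, 30, 36 and 42 (Protocol 6.1 to 6.13).

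**Bottles per full-term subject.** Assume whole bottles and no carry-over.
- Two 84-day intervals: 168 capsules each, so 2 bottles each = 4.
- Seven 168-day intervals: 336 capsules each, so 4 bottles each = 28.
- Total 4 + 28 = 32, of which 2 + 2 + 4 + 4 + 4 = 16 are dispensed before Month 24.
- Pooled over the whole period, the minimum is 2 × 1344 / 100 = 26.9, or 27 bottles.

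**Effect of one lost bottle.** Expected capsules are 2 × 1344 = 2688. The gap between the lower and upper limit is 100 / 2688 = 3.7 percentage points per lost bottle.

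**Share excluded from the mean and median.** With an assumed independent loss probability p per bottle and N bottles, the share is 1 − (1 − p)^N.

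| p per bottle (assumed) | N = 16 (to Month 24) | N = 32 (to Month 48) |
|---|---|---|
| 0.1% | 1.6% | 3.2% |
| 0.5% | 7.7% | 14.8% |
| 1% | 14.9% | 27.5% |
| 2% | 27.6% | 47.6% |
| 5% | 56.0% | 80.6% |

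Half of full-term subjects are excluded only when p reaches about 2.1%. If losses instead cluster by visit, with 9 return occasions, the share is 1 − (1 − q)^9: 8.6% at q = 1% per visit and 37.0% at q = 5%.

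**Banded table, full-term subjects.** Suppose the lost bottles had in fact been emptied. The lower limit then falls 3.7 points per lost bottle, and the subject stays in the 80–120% band while it is at or above 80%.

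| True compliance | Lost bottles tolerated | Share not classifiable at p = 2%, N = 32 |
|---|---|---|
| 100% | 5 | 0.004% |
| 95% | 4 | 0.04% |
| 90% | 2 | 2.6% |
| 85% | 1 | 13.4% |

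**Banded table, a subject lost to follow-up.** Protocol 3.6 lists loss to follow-up as a withdrawal reason, and such a subject would ordinarily keep the bottles last dispensed. As an illustration, take a fully compliant subject who receives 4 bottles at Month 12 (Day 336), takes the last dose on Day 420 and does not return.
- Expected: 2 × 420 = 840 capsules. Accounted for up to Month 12: 2 × 336 = 672.
- Lower limit: 672 / 840 = 80%.
- Upper limit: (672 + 400) / 840 = 1072 / 840 = 128%.

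The range crosses 120%, so this subject appears in neither the continuous nor the banded summary.

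**The case against.** The strongest reply is that the plan already handles this sensibly. The rule is pre-specified. Because capsules taken is dispensed minus returned, a lost container with no special rule would count as fully used; setting the value to missing avoids that upward error. The banded table uses the limits, and with a band 40 points wide against 3.7 points per bottle it keeps nearly every well-adherent full-term subject. The listing shows each affected subject's range with capsules dispensed and returned. SAP 8.2 reports n, so exclusions can be read from n against the size of the safety set. Compliance is not an endpoint, no safety analysis is conditioned on it, and duration and days on treatment do not depend on returns. A forgotten bottle can also come back at a later visit.

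All of that stands, and it limits the point to the continuous summaries. A reader might go further and infer that many subjects will drop out, that compliance will be reported mainly for careful returners, or that the mean will be inflated. The documents support none of these. They give no loss rate; the banded table retains most full-term adherent subjects; and a discarded empty bottle may mean full use just as a missing bottle may mean poor use.

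The reply leaves three gaps. The banded table says only that such subjects may be counted. It fails for subjects near 80% and for some early withdrawals, whose smaller denominators make each lost bottle count for more. And under the default in SAP 8.2, percentages use non-missing data, so subjects who cannot be classified leave the denominator as well.

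**Conclusion.** The point holds for the mean and median of capsules taken and compliance: under SAP 9.5 they are complete-return statistics. For a full-term subject the rule can discard a value known to within 3.7 points because one of about 32 bottles is missing.

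The share affected cannot be stated from the documents. It runs from 3% to 81% of full-term subjects over an assumed independent loss of 0.1% to 5% per bottle, and is smaller if losses cluster by visit or subjects leave early. The direction of any bias is unknown.

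The bottle count rests on whole bottles per interval with no carry-over. The presentation from the start of REN001 treatment adds containers from REN001-201, whose pack size is not given, so these figures apply to REN001-202 dispensing only. This is a cheap improvement in reporting and does not threaten the primary safety conclusions.

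**What to change.** In SAP 9.5, replace the exclusion sentence with wording to this effect:

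> Capsules taken and treatment compliance will be summarized for all subjects in each safety analysis set, once at the lower limit (nothing taken from unreturned containers) and once at the upper limit (everything taken from them). The two limits are equal for subjects with complete returns. The number of subjects with any unreturned container will be presented.

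Keep the banded table. The complete-return summary may stay alongside as an optional extra.

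Both limits are already derived for the listing, so no new data and no assumption about loss rates are needed. If losses are rare, the two rows will nearly coincide and show that the result is robust; if they are common, the gap between the rows will show it. The cost is a short SAP edit and an extra pair of table rows, with a wide range for some early withdrawals.
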